Page 27 Statistical Considerations Original: ...Furthermore, we will use decision trees for identifying the importance of MyoStrain cardiac features compared to cardiac toxicity risk prediction based on standard assessment of variables LVEF, LVESV, and LVEDV... Original: The sensitivity, specificity, and diagnostic accuracy of each reader to detect changes in myocardial function will be determined for quantitative SENC-CMR. Cutoff-values used to calculate sensitivity and specificity of the quantitative SENC parameters will be determined using data previously published. McNemar's test with continuity correction will be used to compare the diagnostic performance of each of the SENC-CMR cutoff parameters. Additionally, Receiver Operating Characteristic curves will be generated to calculate and compare the area under the curves to determine the diagnostic performance of changes in various strain parameters. Inter- and intra-observer variability will also be determined for each of the above parameters using intraclass correlation.	Page 30 Statistical Considerations Modified: ...Furthermore, we will use decision trees for identifying the importance of MyoStrain cardiac features compared to cardiac toxicity risk prediction based on standard assessment of variables LVEF, LVESV, and LVEDV, and LV Stroke Volume Index (LWSVI) . Endpoints will be evaluated based on discrete variables of MyoStrain values versus standard assessments. Considering many patients will have a complex management of cardioactive medications as well as cancer treatment regimen, the classification of cardiotoxicity status will be based on a clinical committee to designate whether the patient experienced no cardiotoxicity, functional decline without cardiotoxicity, subclinical cardiotoxicity, or clinical cardiac dysfunction at each exam time point... Modified: The sensitivity, specificity, and diagnostic accuracy of each reader to detect changes in myocardial function will be determined for quantitative SENC-CMR. Cutoff-values used to calculate sensitivity and specificity of the quantitative SENC parameters will be determined using data previously published. The cutoff for the % of MyoStrain segments <= -17% (based on 37 left ventricular segments) in detecting subclinical cardiotoxicity in the PREFECT50 planned interim analysis was 68% and the cutoff for detecting clinical cardiac dysfunction was 49%; a cutoff of 80% differentiates normal cardiac function from patients experiencing functional decline. McNemar's test with continuity correction will be used to compare the diagnostic performance of each of the SENC-CMR cutoff parameters. Additionally, Receiver Operating Characteristic curves as well as Precision Recall curves will be generated to calculate and compare the area under the curves to determine the diagnostic performance of changes in various strain parameters and standard assessments . Inter- and intra-observer variability will also be determined for each of the above parameters using intraclass correlation.

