11. STATISTICAL CONSIDERATIONS

The data of cardiac features measured will be stored in a WUSTL REDCap-supported database and transformed into a SAS, R, excel, and CSV dataset, so they can be analyzed by our team using SAS, R and PYTHON software packages.

At baseline and any other visit, the standard descriptive statistics will be used to summarize numeric variables, including the number of observed values, mean, standard deviation, median, minimum and maximum values. Summaries of categorical variables will include the number and percentage of observed values, at each level of the categorical variable. Baseline and demographic information will be summarized with standard descriptive statistics.

There will be more than 60 cardiac 3D features measured for each patient (subjects' n=102) resulting from use of MyoStrain SENC software, as shown in the schematic Figure 5. The results will be stratified based on the patient's segmental strain (longitudinal and circumferential) profile with -10% or -17% as the threshold to determine segmental dysfunction and the number of dysfunctional segments delineating patient risk. The patients will be selected at baseline for high cardiovascular risk, which will be important in cancer patients in responding to cardiotoxicity.

Patients will be separated by randomization into two groups. Those of whom the cardiac care will be served with prior knowledge of MyoStrain SENC data as measured in each visit, while the other half, with exception of 4 cardiac measures, they and their doctor will not have knowledge for the full cardiac features, but we will have access to these data also, only at the end of the study.

[figure not shown]

Figure 5: A schematic of measurements and statistical methods to be used for inferring for cardiotoxicity from results of baseline and also at 1, 3, 6, 12, 24 and 36 months' follow-up.

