The longitudinal data will be compared for each individual with his/her baseline, to learn and guide each individual's care and to infer the level of cardiotoxicity. The same group's data will be analyzed with the intention in identifying what trends exist among those in the group of MyoStrain SENC software guided treatment. The full cardiac measures for the other group: the observational arm will be available to us at the end of the trial. At that time, we will analyze also the longitudinal cardiac 3D features for this group at the individual levels compared to baseline. In addition, we will analyze the longitudinal data to identify trends for each group, as well as we will compare trends of two groups toward cardiac response to chemotherapy and / or radiology. We will test the cardiotoxicity development i.e. myocardial dysfunction by comparing the efficacy of detecting cardiac dysfunction using standard assessments LVEF, LVESV and LVEDV in time against analyzing all cardiac features collected via MyoStrain (more than 60 of them, Figure 5). Multivariate regression and logistic regression will be used with "stepwise" option to identify significant predictors at standard and guided care features for predicting cardiotoxicity. Furthermore, we will use decision trees for identifying the

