importance of MyoStrain cardiac features compared to cardiac toxicity risk prediction based on standard assessment of variables LVEF, LVESV, LVEDV, and LV Stroke Volume Index (LVSVi). Endpoints will be evaluated based on discrete variables of MyoStrain values versus standard assessments. Considering many patients will have a complex management of cardioactive medications as well as cancer treatment regimen, the classification of cardiotoxicity status will be based on a clinical committee to designate whether the patient experienced no cardiotoxicity, functional decline without cardiotoxicity, subclinical cardiotoxicity, or clinical cardiac dysfunction at each exam timepoint. The last analysis will help to identify also any indication for interactions among variables studied. We will implement Intention-To-Treat-analysis, where the analyses of the two groups will be based on the initial treatment assignment in the two randomized groups. If in the follow-up data-points may be missing, we will check if the missing data-points are random and if several covariates can help in imputation of missing. We plan to use MI procedure of SAS Institute for such imputations. The regression will be implemented via GLM, LOGISTIC and MIXED (for statistical analysis of repeated measures) procedures in SAS. For mixed models, a comparison of models will be done via likelihood ratio test and by using the Akaike Information Criterion (AIC) and Schwartz's Bayesian Criterion (SBC). Graphical presentations will be implemented in R via LMER of LME4 mixed modelling build in functions, and specialized software GGPlot2 in R. Decision (known also as partition) trees will be implemented with SAS-Data Mining software. We will use also PYTHON-scikit machine learning package for testing the performance of partition-trees via random forest. A random forest is a meta estimator that fits a number of decision tree classifiers on various sub-samples of the dataset and use averaging to improve the predictive accuracy and control overfitting.

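### The tree comparison of more than 60 MyoStrain features with four standard measures has no safeguard against the unequal counts, and leans towards MyoStrain unless a standard measure predicts strongly

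*Combined protocol and SAP*

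**What the plan says.** All of this stands in the current Section 11 (Statistical Considerations); the amendment log only repeats it.

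- **Candidates.** "There will be more than 60 cardiac 3D features measured for each patient". Detection by the standard measures is to be set against "analyzing all cardiac features collected via MyoStrain (more than 60 of them, Figure 5").
- **Purpose of the trees.** "we will use decision trees for identifying the importance of MyoStrain cardiac features compared to cardiac toxicity risk prediction", where that prediction rests on four standard measures: LVEF, LVESV, LVEDV and stroke volume index. The text does not say whether all features enter one tree or whether two models are compared.
- **Possible overlap.** For the observational arm, "with exception of 4 cardiac measures, they and their doctor will not have knowledge for the full cardiac features". This may count the four standard measures among the 60-plus, which would leave about 56 against 4.
- **Forest.** A random forest is added to check how well the partition trees perform. Its averaging is described as improving accuracy and limiting overfitting. No ranking of features by the forest is planned.
- **Sample size.** Section 5.7 gives 40 evaluable patients; Section 11 still carries 102.

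The text names no importance metric, cross-validation, permutation null or adjustment for unequal numbers of candidates. Figure 5, a schematic of measurements and methods, is not shown in the copy read.

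**The concern.** A tree splits on whichever candidate separates the classes best in the sample at hand. With 60 tickets against four, the best of many uninformative MyoStrain features can beat a real but moderate standard predictor, especially in 40 patients. Averaging over trees steadies predictions, but it does nothing about one side having fifteen times as many candidates (60/4 = 15).

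Primary objective 2 asks whether MyoStrain detects subclinical dysfunction better than standard imaging. A tree result that favours MyoStrain partly because of candidate numbers would be read as support for that objective.

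**Working it through.** **1. The plan's own figure.** Section 11 gives no figure for the tree step. Its sample size is for the 6-month count of dysfunctional segments. The difference is 16.8 − 12.8 = 4.0 and the SD is (4.7 + 7.8)/2 = 6.25, with 90% power and 5% two-sided (sidedness assumed). Total N = 4 × [6.25 × (1.960 + 1.282)/4.0]² ≈ 102.6, so the stated 102 reproduces. It gives no assurance about the trees.

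**2. No signal anywhere.** If features are exchangeable, the chance that a MyoStrain feature ranks first is m/(m + 4): 60/64 = 93.8%, or 56/60 = 93.3% if the four measures are among the 60. With equal blocks it is 4/8 = 50%.

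**3. LVEF informative, MyoStrain pure noise.** Assumed, not in the documents: binary outcome, 12 events in 40 patients, 60 MyoStrain features with pairwise correlation 0.3, Gini split. An AUC converts to a shift in SD by d = √2 × z(AUC); for example 1.414 × 0.524 = 0.74 at AUC 0.70. Ranges are over separately coded runs.

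| LVEF AUC | Shift (SD) | First split on MyoStrain, 60 v 4 | Same, 4 v 4 |
|---|---|---|---|
| 0.50 | 0 | about 93% | about 50% |
| 0.70 | 0.74 | 66–71% | about 25% |
| 0.80 | 1.19 | 30–36% | 6–7% |
| 0.90 | 1.81 | about 4% | – |
| 0.95 | 2.33 | under 1% | – |

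At AUC 0.70, varying the correlation from 0.6 to 0 moves the 60 v 4 rate over 61–74%.

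**4. Sensitivity to sample size.** A second simulation used 30% prevalence and MyoStrain correlation 0 to 0.5, with 1,000 runs per setting. First split on MyoStrain:

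| LVEF shift (SD) | n = 40 | n = 102 |
|---|---|---|
| 0 | 90–94% | 88–93% |
| 0.5 | 81–88% | 61–71% |
| 1 | 51–58% | 10–11% |
| 1.5 | 14–21% | under 1% |
| 2 | 4% | under 1% |

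The problem is larger at the current 40 than at 102.

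**5. Two separate models instead of one ranking.** Results depend on whether performance is in-sample.

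| LVEF AUC | Noise MyoStrain tree wins, in-sample AUC (depth 3) | Noise MyoStrain forest wins, 5-fold cross-validated AUC |
|---|---|---|
| 0.50 | 95% | 48% |
| 0.70 | 87% | 23% |
| 0.80 | 63% | 5% |

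The cross-validated column rests on 60 runs per setting. Cross-validation removes the lean; the plan does not call for it.

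**6. Importance measures, should they be used.**
- Forest importance summed over the MyoStrain block is 75–94% of the total in every setting of step 4, even with a 2 SD LVEF shift.
- Averaged per feature there is no systematic MyoStrain advantage: MyoStrain exceeds the standard mean in 32–60% of runs with no signal and 0–2% at 2 SD.
- Ranking single features on held-out patients does not cure it. At AUC 0.70 the top feature is still noise MyoStrain in 70–73% of runs (30 and 100 runs).
- Grouped held-out importance without a null favours the noise block in 50% of runs at 60 v 4 (AUC 0.70), against 26% at 4 v 4.
- Judged against a label-permutation null, noise MyoStrain is declared important in 3.5% of runs at the 5% level at 60 v 4.

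**The case against.** A reader might infer that MyoStrain must come out on top by numbers alone. The documents do not support that. Section 1.5 puts LVEF change into the definition of clinical cardiac dysfunction and of subclinical cardiotoxicity, so a high LVEF AUC is plausible, and at 0.90 or above the effect nearly vanishes. Worsening GLS is also a criterion there and MyoStrain reports a GLS, so a wholly uninformative MyoStrain set is an extreme case. It tests the method; it does not forecast the trial.

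A reader might also take the forest as a planned importance ranking. Section 11 gives it only a performance-testing role, so the forest figures in step 6 apply only if importance is in fact read from it.

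The joint ranking is one reading; a comparison of two models is equally open. This limits the claim without removing it, because the in-sample version of that comparison leans the same way and no out-of-sample version is specified.

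The simulations use one binary outcome per patient. The plan has a four-level committee classification at up to seven exams (baseline and six follow-ups), and the event rate is unknown. The percentages are therefore indicative.

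Finally, the primary endpoint does not rest on the trees. Section 11 gives it published cutoffs for the share of segments (80%, 68% and 49%) and ROC and precision-recall comparisons. That stands, and it limits the importance of the point.

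**Conclusion.** The point holds in a conditional form. Section 11 leaves the MyoStrain-versus-standard tree comparison without a stated model structure, metric, validation or null. Under the joint-ranking reading or the in-sample two-model reading, the result leans towards MyoStrain when the standard measures predict weakly or moderately, and hardly at all when one of them predicts strongly. The size runs from about 93% of first splits with no signal to about 4% at an LVEF AUC of 0.90, given the assumed event rate, correlation and uninformative MyoStrain features. It is a supporting analysis for primary objective 2. The change should be made before the data are analysed, but the primary endpoint analyses are not undermined.

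**What to change.** State in Section 11 that the MyoStrain-versus-standard comparison will use one of two methods:

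- cross-validated performance of a model with the standard measures alone and of one with the MyoStrain set added; or
- held-out grouped permutation importance, with each set permuted as a whole.

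In either case split the folds by patient, since patients contribute repeated exams, and judge the result against a null obtained by permuting the cardiotoxicity labels through the whole procedure. Label any tree or forest ranking of the 60-plus features as hypothesis-generating, with no MyoStrain-versus-standard conclusion drawn from it.

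An optional sensitivity analysis could use a small pre-specified MyoStrain block: number of segments above −17%, number above −10%, GLS and GCS. Equal block sizes are not essential once the null is in place.

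The cost is SAP wording and a little more analysis work, with no new data. The MyoStrain result may look less favourable.

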1. SUMMARY

1.1. Study Purpose

This study is intended to evaluate the ability of a new analysis package with cardiac MRI to assist in the early detection and management of cardiotoxicity from therapeutics used to treat cancer.

1.2. Study Device and Intended Use

Common Name: Cardiac MRI Imaging Software

Trade Name: MyoStrain®

Regulatory Status: The MyoStrain® SENC CMR Imaging System is limited to observational evaluation within the United States. MyoStrain® has European approval with an EC Certificate according to Directive 93/42/EEC on Medical Devices, Annex II excluding Section 4 (CE 657862) in respect of: Design, development and manufacture of software for the quantification of cardiac MRI images.

Intended Use: MyoStrain® SENC software receives image data from MRI storage archives and performs viewing, image manipulation, communication, printing, and quantification of images. Available measurements include longitudinal and circumferential strain to quantitatively describe the wall motion of the heart. Tools are provided for display of regional motion properties of the heart.

A report interface is provided. Measurement tools provide information that can be output in standardized or specialized report formats. This interface makes it possible to quickly and reliably fill out a complete clinical report of a cardiac imaging exam with strain. The results of the measurement tools are interpreted by the physician and can be communicated to referring physicians to support the determination of a diagnosis.

1.3. Study Design

This is a prospective, multi-center, open label, randomized study. The study will enroll patients who exhibit subclinical myocardial dysfunction at baseline as determined by MyoStrain® evaluation.

Patients with any type of cancer scheduled to receive anti-cancer therapy, who are previously enrolled in the SURVIVE Registry, will be screened for study participation. Consented subjects meeting all inclusion/exclusion criteria will be enrolled into the PROACT study. Subjects will be randomized 1:1 between the MyoStrain® guided treatment arm and MyoStrain® observational arm. Patients in both randomized study arms will be followed with MyoStrain® testing at baseline, 1, 3, 6, 12, 24 & 36 month follow-ups, as outlined in the protocol.

1.4. Objectives

The primary objectives of this study are:

1. to robustly quantify myocardial function in cancer patients scheduled to receive anti-cancer therapy
2. to determine the ability of MyoStrain® testing to detect subclinical cardiac dysfunction compared to standard cardiac imaging
3. to determine the impact of MyoStrain® imaging on medical management of cardiotoxicity through early detection of at risk patients

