1.5. Endpoints

The primary efficacy endpoint is the sensitivity and accuracy of detection of patients with myocardial dysfunction using MyoStrain® compared to standard assessments of cardiac function: left ventricular ejection fraction (LVEF), as well as end-systolic (LVESV), end-diastolic (LVEDV), and stroke (LVSV) volumes indexed to body surface area.

Changes in function based on clinical presentation, standard assessments, and all available metrics will be used to define the cardiotoxicity status of the patient. A clinical committee organized and chaired by the principal investigator will be used to classify each exam in both unblinded and blinded arms according to professional knowledge and derived from the ASE Expert Consensus Position Paper, the ESC Position Paper, and the ESMO Clinical Practice Guidelines. [1] [2] [3]

- Clinical cardiac dysfunction is defined as an absolute change in LVEF > 10% from baseline to below 53% combined with heart failure symptoms or abnormal cardiac biomarkers (troponin, BNP, or NT pro BNP).
- Subclinical CTX was defined as an asymptomatic patient with a greater than 15% decrease in LVEF that remains >= 53%, worsening GLS more than 15% from baseline, or abnormal cardiac biomarkers (troponin, BNP, or NT pro BNP).
- If no baseline information is available to compare metrics for categorizing cardiotoxicity status, considering most patients in the PROACT sub-study of the Survive Registry will have metastatic cancer with prior treatments including chemotherapy, physician discretion and patient presentation will provide the final decision on cardiotoxicity category. All available metrics will be used to classify patients at each assessment time point.

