5. STUDY DESIGN

5.1. Summary Protocol

Patients with any type of cancer scheduled to receive anti-cancer therapy with or without concomitant radiotherapy and enrolled in the SURVIVE Registry will be evaluated based on baseline MyoStrain® segmental dysfunction risk profile. After consenting to the PROACT study, patients will undergo a baseline MRI to determine their risk stratification for the study. This baseline MyoStrain® MRI must demonstrate 2 or more segments measuring >-10% or 9 or more segments >-17% for entrance into the study.

[figure not shown]
Eligible patients will then be randomized 1:1 into the MyoStrain® guided treatment arm versus the Myostrain® blinded observational arm, as shown in Figure 2. The treatment arm will guide patient management by augmenting standard of care with serial MyoStrain® monitoring of the impact of cancer therapy on myocardial function by providing physicians with MyoStrain® values, in addition to LVEF, LVEDV, and LVESV. In the

observational arm, physicians will only be provided with LVEF, LVEDV, and LVESV, which are clinical measurements. The standard of care assessments by cardiac MRI, will not include MyoStrain® assessments.

In order to obtain the MyoStrain® values, MRI images obtained will be uploaded de-identified to Myocardial Solutions, Inc. After the baseline scan, Myocardial Solutions, Inc. will inform research staff whether the patient met criteria for continued follow up in the study. At that time, the patient will be randomized to one of the two arms, as previously described, and Myocardial Solutions, Inc. will be made aware of the randomization result. If randomized to the blinded observational arm, no results from any cardiac MRI obtained for the study will be provided to physicians from Myocardial Solutions, Inc. If randomized to the MyoStrain® guided treatment arm, MyoStrain® results and LVEF, LVEDV, and LVESV will be provided for all cardiac MRI's obtained in the study to the physicians. Sites will also send Myocardial Solutions, Inc. de-identified information about the patients' medical history (i.e. comorbidities, past/current medications, etc.).

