Based on pilot data and utilizing only the moderate to high risk group (>2 segments of Myostrain determined segments >17%), the outcome expected would be 12.8 +/- 4.7 dysfunctional segments for the intervention group and 16.8 +/- 7.8 dysfunctional segments for the control group (and using average of 4.7 and 7.8 for the standard deviation for the overall outcome) at 6 months. This same parameter will be followed at the other time points, including 1 year, 2 years, and 3 years, but the primary endpoint will be at 6 months. With these calculations, 102 patients are required to have a 90% chance of detecting, as significant at the 5% level, a decrease in the primary outcome measure from 16.8 in the control group to 12.8 in the experimental group (number of dysfunctional segments (>17%)).

The sensitivity, specificity, and diagnostic accuracy of each reader to detect changes in myocardial function will be determined for quantitative SENC-CMR. Cutoff-values used to calculate sensitivity and specificity of the quantitative SENC parameters were determined using data previously published. The cutoff for the % of MyoStrain segments <= -17% (based on 37 left ventricular segments) in detecting subclinical cardiotoxicity in the PREFECT50 planned interim analysis was 68% and the cutoff for detecting clinical cardiac dysfunction was 49%; a cutoff of 80% differentiates normal cardiac function from patients experiencing functional decline. McNemar's test with continuity correction will be used to compare the diagnostic performance of each of the SENC-CMR cutoff parameters. Additionally, Receiver Operating Characteristic curves as well as Precision Recall curves will be generated to calculate and compare the area under the curves to determine the diagnostic performance of changes in strain parameters and standard assessments. Inter- and intra-observer variability will also be determined for each of the above parameters using intraclass correlation.

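### Primary objective 3, the effect of imaging on medical management, has no management outcome; the only powered between-arm outcome is segment count at 6 months

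*Combined protocol and SAP*

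**What the plan says.** Sections 1.4 and 3 list three primary objectives in the same words. The third is "to determine the impact of MyoStrain® imaging on medical management of cardiotoxicity through early detection of at risk patients".

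Section 1.5 states: "The primary efficacy endpoint is the sensitivity and accuracy of detection of patients with myocardial dysfunction using MyoStrain", judged against LVEF and ventricular volumes. It adds a committee that classifies cardiotoxicity status at each exam.

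Section 11 compares the randomised arms on a different quantity. It expects "12.8 +/- 4.7 dysfunctional segments for the intervention group and 16.8 +/- 7.8 dysfunctional segments for the control group", says that "the primary endpoint will be at 6 months", and sizes the trial to detect "a decrease in the primary outcome measure from 16.8 in the control group to 12.8 in the experimental group". It also compares longitudinal trends in cardiac features between arms and specifies intention-to-treat analysis. Medication is mentioned there only as a reason for having a committee classify cardiotoxicity.

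Section 5.1 makes the arms differ in what physicians are shown. Its example principles for acting on the results are to consider cardioprotective treatment, advise oncology and educate the patient. None is mandatory, and Section 7.2 leaves decisions to physicians using all available information. The schedule of events lists consent, eligibility, MRI, randomisation and a satisfaction questionnaire. Sites send the vendor medical history, described as "i.e. comorbidities, past/current medications, etc". No follow-up collection, REDCap entry or analysis of that information is stated.

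**The concern.** A primary objective should have a variable that answers it, collected on a schedule and compared in the analysis. Objective 3 has none. If the plan is followed exactly, the final report can describe diagnostic performance and segment counts by arm, but not whether physicians who saw MyoStrain results managed patients differently.

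This matters for interpretation because the intervention is information. It can alter segment counts only if someone acts on it, and nothing in the protocol requires action. If the arms have similar segment counts at 6 months, two explanations remain open: guidance did not change care, or care changed and function did not respond. These point to different next steps, and the planned data do not separate them.

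**Working it through.** **1. Trace each primary objective to an outcome.**

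| Objective | Outcome in the plan | Uses the randomised comparison? |
|---|---|---|
| 1. Quantify myocardial function | Descriptive and longitudinal strain summaries (Section 11) | Not needed |
| 2. Detect subclinical dysfunction compared with standard imaging | Sensitivity and accuracy (Sections 1.5 and 11) | No |
| 3. Impact on medical management | No management variable in Section 1.5, the schedule of events or Section 11 | – |

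The powered randomised outcome, segment count, measures function. Section 4 links management to restoring myocardial function, so segment count is a possible consequence of a management change. It is not a record of one.

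**2. Reproduce the plan's sample size.** Inputs from Section 11:
- Difference: 16.8 − 12.8 = 4.0 segments.
- SD: "using average of 4.7 and 7.8 for the standard deviation for the overall outcome", so (4.7 + 7.8)/2 = 6.25.
- Target: "102 patients are required to have a 90% chance of detecting, as significant at the 5% level". Sidedness is not stated; two-sided is used here.

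n per arm = 2 × (1.960 + 1.282)² × 6.25² / 4.0² = 51.3, rounded up to 52, or 104 in total. The stated 102 (51 per arm) has 89.8% power by the normal formula, so the plan's figure reproduces. One-sided 90% power would need 84 in total and two-sided 80% power would need 78, so two-sided 90% is the reading that fits.

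**3. Power for segment count at the current size.** Section 5.7 gives 40 evaluable patients randomised 1:1, so 20 per arm.
- SE of the difference = 6.25 × √(2/20) = 1.976.
- Power = Φ(4.0/1.976 − 1.960) = Φ(0.064) ≈ 53% (51% by t-test).
- Difference detectable with 80% power = (1.960 + 0.842) × 1.976 ≈ 5.5 segments, against the planned 4.0.

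Even if the planned effect is real, the chance of a non-significant result is about 100 − 53 = 47%. The gap between 102 in Section 11 and 40 in Section 5.7 is a separate matter; it is used here only to show how likely an ambiguous null is.

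**4. What a management outcome could deliver with 20 per arm.** The documents give no rate for any management event, so the rates below are assumptions. Two-sided 5% level. Normal approximation with p̄ the mean of the two rates:

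Power = Φ{[|p₂ − p₁| − 1.96√(2p̄(1 − p̄)/20)] / √[(p₁(1 − p₁) + p₂(1 − p₂))/20]}

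| Assumed control v guided | Normal approximation | Fisher exact |
|---|---|---|
| 20% v 40% | 28% | 19% |
| 20% v 50% | 51% | 41% |
| 25% v 60% | 62% | 49% |
| 20% v 70% | 92% | 85% |

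Worked line for 25% v 60%: p̄ = 0.425, so Φ[(0.35 − 1.96 × 0.1563)/0.1462] = Φ(0.298) ≈ 62%.

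95% CI half-width for 25% v 60% = 1.96 × √(0.25 × 0.75/20 + 0.60 × 0.40/20) = 0.287, about 29 percentage points.

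**The case against.** The strongest reply is that the randomised question does have a compared outcome. Section 11 compares the arms on segment count at 6 months, calls it the primary endpoint and sizes the trial on it, with analysis by assigned arm. Read with Section 4, segment count is the plan's test of whether guided management worked, and what is missing is a process measure. This stands. A reader might infer that randomisation serves no compared outcome at all; Section 11 contradicts that. It does not rescue objective 3 as worded, which asks about management.

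A reader might also infer that a positive result could not be credited to guidance without management data. That does not follow. An intention-to-treat difference between randomised arms is attributable to assignment to guidance, whether or not the intermediate step is recorded. Only the route would be unknown.

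A third tempting inference is that the data already arrive and need only be analysed. Section 5.1 does not support it. Medications are mentioned as medical history sent to the vendor, with no dates or follow-up schedule, and changes to cancer treatment are not named. The SURVIVE Registry may hold more, but its protocol is not among these documents.

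Finally, the proposed outcome is open to the criticism that, in an open-label study, a medication start or change partly records that a report was acted on. That is a fair limit on interpretation, although acting on the report is close to what objective 3 asks about.

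**Conclusion.** The point holds in this form: objective 3 has no management outcome defined, scheduled or compared, so the plan as written cannot answer it. The powered segment-count comparison is a valid randomised outcome but sits downstream of management. The practical loss falls mainly on a null result, which has about a 47% chance of occurring at 20 per arm even if the planned 4-segment effect with SD 6.25 is true. Such a null could not be separated from guidance never having altered care.

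The absence of a management outcome rests on the text and on no assumed figure. The 53% power rests on the plan's own difference and SD, two-sided 5%, and 40 evaluable patients split equally. The power and precision of any added management outcome rest on assumed rates and are limited. Exact-test power runs from 19% to 85% across the range shown, and it reaches 80% only for the 50-point difference. The added outcome should therefore be reported as an estimate, not as a decisive test.

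**What to change.** Add to Sections 1.5 and 11 two between-arm intention-to-treat comparisons, each a risk difference with 95% CI and described as estimation:
- the proportion with any recorded start or change of cardioprotective medication by 6 months;
- separately, the proportion with any recorded modification of cancer therapy by 6 months.

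Add a dated REDCap field for these events to the schedule of events at the visits already planned. It can be completed from the medical records that Sections 12 and 15.2 already require sites to keep. If the SURVIVE Registry already captures the events with dates, cite that source and add only the analysis. State beside the results that treating physicians knew the arm. If the sponsor does not want to collect these data, the alternative is to stop listing objective 3 as primary.

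The cost is a small protocol amendment, some data entry, and chart abstraction for visits already held. No scan, visit or clinical instruction is added. This is a cheap improvement.
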